6.2.2.5. Re-deploying Revascularization Device

If the revascularization device should be re-deployed (e.g., repositioning), take the following steps:

- ✧ Warning: When the device has been combined with thrombus, pushing the microcatheter may result in embolization fragments. No resistance encounters when advancing the microcatheter.
1. Loosen the RHV around the microcatheter and around the push rod. With the help of radiographic monitoring, securely fix the push rod to prevent the revascularization device from moving.
 2. Carefully advance the microcatheter forward to the distal end of the revascularization device until the distal marker of the thrombectomy stent is aligned with the distal end of the microcatheter to complete re-sheathing. If great resistance encounters during one more sheathing, stop immediately. Proceed to the above "Withdrawing Revascularization Device" section.

6.2.2.6. Precautions

- Only physicians trained in neurointerventional techniques and ischemic stroke can use this device.
- Inspect packaging and devices for damage in transit prior to use. Please do not use a bent or damaged device.

- Use before the "Shelf-life" indicated on the label.

6.2.2.7. Contraindications

- Patients who are known to be allergic to nickel titanium alloy.
- Patients with stenosis near the thrombus site and/or pre-existing stents, since safe withdrawal of a revascularization device may be hindered.
- Patients with angiographic evidence of carotid artery dissection.

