6.1.5.2. Exclusion criteria

General exclusion criteria:

- 1) Those who could undergo neither MRI nor CT;
- 2) Those with hemorrhagic stroke or major ischemic stroke within 6 months before enrollment;
- 3) Those with severe persistent hypertension that could not be controlled by intravenous injection for blood pressure reduction, i.e. patients with sustained SBP > 185 mmHg or sustained DBP > 110 mmHg;
- 4) Those with presumed septic emboli or suspected bacterial endocarditis;
- 5) Renal failure, defined as creatinine > 3.0 mg/dL ($264 \mu\text{mol/L}$);
- 6) Those with blood glucose < 2.78 mmol/L (50 mg/dL) or > 22.20 mmol/L (400 mg/dL);
- 7) Decreased platelet count ($< 40 \times 10^9/\text{L}$);
- 8) Those with known hemorrhage tendency, coagulation factor deficiency, are taking anticoagulants and with INR > 3.0 ;
- 9) Pregnant or lactating women;
- 10) Those with known severe allergy to contrast media or known allergy to nickel materials;
- 11) Those with disorders possessing possibility of affecting neurological assessment (e.g., neurological and psychiatric disorders);
- 12) Those with heart, lung, liver failure or other serious disorders leading to disablement of interventional operation;

- 13) Participating in clinical trials of other drugs or devices;
- 14) Life expectancy less than 6 months;
- 15) Other conditions judged by the investigator to be not suitable for inclusion.

Angiographic exclusion criteria:

- 1) There is evidence of intracranial hemorrhage on CT or MR or known hemorrhage tendency;
- 2) CT/MR/DSA angiography suggests > 1 vascular occlusion (e.g., simultaneous occlusion of bilateral internal carotid artery vessels, or simultaneous occlusion of intracranial vessels in anterior and posterior circulation, or simultaneous occlusion of intracranial and extracranial internal carotid artery);
- 3) Those with carotid artery dissection, occlusion of the initial segment of the carotid artery or arteritis;
- 4) Those whose access vessels are quite tortuous, making the revascularization device difficult to reach the target location.

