6.1.6. Effectiveness Evaluation Methods

- 1) Description of effectiveness endpoints
 - a) Primary effectiveness endpoint: success rate of instant recanalization
 - b) Secondary effectiveness indicators: Proportion of subjects with mRS scores of 0-2 on 90d postoperatively, time from femoral artery puncture to recanalization/the end time of operation for subjects whose recanalization failed, proportion of subjects with NIHSS score decrease > 4 , and success rate of device operation
- 2) Selection of Method and Time to Evaluate, Record and Analyze Effectiveness

Indicators

Primary endpoint:

● Success rate of instant recanalization

Recording time and method: During thrombectomy, cerebral vascular DSA examination will be performed to analyze whether the recanalization success is achieved. If the recanalization is affected due to in situ atherosclerotic stenosis, vascular dissection and vasospasm after thrombectomy, the investigator can handle it in an appropriate way and determine whether the target vessel is successfully revascularized according to the recanalization after treatment.

* Recanalization success was evaluated separately by clinicians and a central interpretation room independent of the study, and when the evaluation results were inconsistent, the results of the blind evaluation by the central interpretation room prevailed.

Formula: Success rate of instant recanalization = Number of subjects with instant recanalization success in this group/Number of subjects treated with revascularization devices in this group $\times 100\%$.

Criteria for instant recanalization success: target vessel recanalization, with mTICI grade of 2b or 3. The mTICI grading is shown in Appendix 3.

Secondary endpoint:

● Proportion of mRS scores of 0-2

Recording time and method: preoperatively and 90 ± 14 d postoperatively. Postoperative subjects' degree of disability will be analyzed by 90-d mRS scores postoperatively. The mRS score is based on mRS scale (as shown in Appendix 4).

Proportion of subjects with mRS scores of 0-2 = Subjects with mRS scores of 0-2 on 90d postoperatively/Number of subjects treated with intracranial thrombectomy device $\times 100\%$.

● Time from femoral artery puncture to recanalization/the end time of operation for patients whose recanalization failed

Evaluation time: Intraoperatively

Evaluation site: target vessel

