6.2.2.9. Warnings

- Appropriate anti-platelet and anti-coagulation therapy should be used in accordance with standard guidelines.
- No twisting of the revascularization device
- For each new revascularization device, use a new microcatheter
- Electrical detachment cannot be performed during thrombectomy

- To prevent device detachment:
 - a. Do not use oversized device.
 - b. Do not withdraw the device if excessive resistance encounters. The device should be re-sheathed with a microcatheter and the entire system should be removed under aspiration. If resistance encounters during one more sheathing, stop entry and remove the entire system under aspiration.
 - c. Do not treat patients with pre-existing stenosis proximal to the thrombus site.
- The device is provided sterile and for single use. Do not re-use or re-sterilize. Reuse and re-sterilization increase the risks of patient infection and compromise device performance.

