6.5. Surgical Record (FAS)

Table21 Target Vessel Surgery Information

Item	Indicator	Experimental Group	Control Group	Total
Number of Target Vessels*	1 n(%)			
	2 n(%)			
	Total (Missing)			
	Statistic			
	P-value			
Number of devices used	1 n(%)			
	2 n (%)			
	Total (Missing)			
	Statistic			
	P-value			

Item	Indicator	Experimental Group	Control Group	Total
Number of Thrombectomy Procedures	N(Missing)			
	Mean (SD)			
	Median			
	Q1, Q3			
	Min,Max			
	Statistic			
	P-value			
Number of Thrombectomy Procedures - Qualitative	1 time n(%)			
	2 times n(%)			
	≥3 times n(%)			
	Total (Missing)			
	Statistic			
	P-value			
Distal Embolism	Yes n(%)			
	No n(%)			
	Total (Missing)			
	Statistic			
	P-value			
Whether underlying stenosis was detected after recanalization	Yes n(%)			
	No n(%)			
	Total (Missing)			
	Statistic			
	P-value			
Use of Recute or Other Auxiliary Therapy	Yes n(%)			
	No n(%)			
	Total (Missing)			
	Statistic			
	P-value			
Stent implantation for recute treatment	Yes n(%)			
	No n(%)			
	Total (Missing)			
	Statistic			
	P-value			
Use of Balloon Dilatation for Recute Treatment	Yes n(%)			
	No n(%)			
	Total (Missing)			
	Statistic			
	P-value			
Other Recute Treatments Used	Yes n(%)			
	No n(%)			
	Total (Missing)			

Item	Indicator	Experimental Group	Control Group	Total
	Statistic			
	P-value			

Note: Except for analyses where the number of target vessels is the subject unit, all other analyses in this table use target vessel units.

Table22 Thrombectomy Device Usage Information (Device Units)

Item	Indicator	Experimental Group	Control Group	Total
Stent Diameter (mm)	N(Missing)			
	Mean(SD)			
	Median			
	Q1, Q3			
	Min,Max			
	Statistic			
	P-value			
Stent Length (mm)	N(Missing)			
	Mean(SD)			
	Median			
	Q1, Q3			
	Min,Max			
	Statistic			
	P-value			
Device Specifications (Diameter × Length) (mm × mm)	3×20 n(%)			
	3×30 n(%)			
	3×40 n(%)			
	4×15 n(%)			
	4×20 n(%)			
	4×30 n(%)			
	4×40 n(%)			
	6×20 n(%)			
	6×30 n(%)			
	6×40 n(%)			
	Total (Missing)			
	Statistic			
	P-value			

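### One device contraindication (stenosis near the thrombus or pre-existing stents) and the related warning on proximal stenosis have no matching eligibility criterion, so Protocol 6.1.5 permits randomisation of patients whom 6.2.2 says not to treat

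*Protocol*

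**What the plan says.** Protocol 6.2.2.7 lists three contraindications. The first is an allergy item: "Patients who are known to be allergic to nickel titanium alloy". The second, which is the subject of this point, reads "Patients with stenosis near the thrombus site and/or pre-existing stents, since safe withdrawal of a revascularization device may be hindered". The third is a vascular finding at baseline: "Patients with angiographic evidence of carotid artery dissection".

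Among the measures against device detachment, Protocol 6.2.2.9 adds: "Do not treat patients with pre-existing stenosis proximal to the thrombus site".

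Two exclusion criteria in Protocol 6.1.5.2, repeated in the abstract, correspond to the first and third contraindications. General exclusion 10 reads "Those with known severe allergy to contrast media or known allergy to nickel materials". Angiographic exclusion 3 reads "Those with carotid artery dissection, occlusion of the initial segment of the carotid artery or arteritis".

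Two other places mention stenosis. The primary-endpoint rule in Protocol 6.1.6 lets the investigator give further treatment and then rate success "If the recanalization is affected due to in situ atherosclerotic stenosis, vascular dissection and vasospasm after thrombectomy". SAP Table 21 (section 6.5) tabulates "Whether underlying stenosis was detected after recanalization".

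**The concern.** A protocol should give one answer to whether a given patient may be treated with the device. Here the device-use section names a finding as a contraindication, on the ground that retrieval may not be safe, and the eligibility section is silent on it.

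Two things are at stake. The first is safety: the hazard is one the protocol itself names, and no eligibility criterion screens for it. The second is the analysed population. A site that screens on 6.1.5 alone and a site that also applies 6.2.2 can enrol different patients. If an operator applies the contraindication only once the allocated device is known, the subject drops out of the analysis after randomisation, in a non-inferiority trial whose operators are not blinded to the device.

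**Working it through.** **1. Match each item in 6.2.2 to the eligibility list and the angiography record.**

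| Item in 6.2.2 | Matching criterion (6.1.5.2 and abstract) | Item in Visit 2 DSA record (6.2.1.3) |
|---|---|---|
| Nickel-titanium allergy (6.2.2.7) | General exclusion 10 | Not an angiographic finding |
| Carotid dissection (6.2.2.7) | Angiographic exclusion 3 | Yes |
| Stenosis near the thrombus and/or pre-existing stents (6.2.2.7) | None | None |
| Pre-existing stenosis proximal to the thrombus (6.2.2.9, item c) | None | None |

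**2. Check the nearest criteria.** Angiographic inclusion 3 requires an acute large-artery occlusion and sets no condition on stenosis or stents. Angiographic exclusion 2 covers more than one occlusion. Exclusion 3 covers dissection, occlusion at the carotid origin and arteritis. Exclusion 4 covers tortuous access. None reaches a non-occlusive stenosis or an old stent. In the SAP, Table 6 records a history of peripheral arterial stenosis, which says nothing about position relative to the clot, and Table 13 (screening angiography) has no such item.

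**3. Check the order of events.** Protocol 6.2.1.1 places randomisation after DSA and before device use. A stenosis or stent visible on that angiogram can therefore be judged before the arm is known.

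**4. Follow a patient with the finding through the analysis rules.**

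- *Excluded before randomisation under general exclusion 15:* no effect on the randomised comparison, but it depends on each investigator's judgement.
- *Randomised, then not treated with the device:* the flowchart note in Protocol 6.2.1.3 (repeated in SAP 1.4) handles the subject as a blank number. The full analysis set (Protocol 8.6, SAP section 3) requires receipt of the product, so the subject is not in it. The investigator sees the allocation under 6.2.1.2. Section 6.2.2 does not say whether its contraindications bind the control arm, so such losses could differ by arm.
- *Randomised and treated:* no named eligibility criterion has been broken, so the subject could also remain in the per-protocol set.

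**5. Scale of the second route.** The planned size reproduces: n = (1.960 + 0.842)² × (2 × 0.89 × 0.11) / 0.125² = 98.36, rounded up to 99; 99 / 0.90 = 110 per group, 220 in total. Protocol 8.1 counts every exclusion from the primary analysis as dropout, so blank numbers would draw on that 10% allowance. With m analysed per group, approximate power is Φ(0.125 / √(2 × 0.89 × 0.11 / m) − 1.960). Taking assumed total losses of 0%, 10% and 20%:

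- m = 110: 84.2%
- m = 99: 80.3%
- m = 88: 75.5%

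These percentages are assumptions, not estimates of how often the finding occurs. Power is protected while total loss stays within 10%. The sample size does not guard against loss that differs between arms.

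**The case against.** The strongest reply is general exclusion 15, which lets an investigator exclude any patient judged unsuitable. An investigator who reads 6.2.2.7 has a direct route to do so before randomisation. This stands in part. A reader might infer that such patients meet all the criteria and must be enrolled, and that is not so. But the item allows exclusion without requiring it and names neither finding, so it narrows the gap without closing it.

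Second, 6.2.2 is headed as a recommended method that the operator may slightly modify. That fits technique. It does not naturally extend to treating a patient who falls under a contraindication or an express warning against treatment.

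Third, a reader might infer that 6.1.6 and SAP Table 21 contradict the contraindication, so that the sections cannot all be followed. The documents do not show this. Both places concern stenosis met after thrombectomy or recanalization, which may not be visible while the vessel is occluded. A site could decline patients with visible stenosis and still need the 6.1.6 rule for stenosis uncovered later.

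Fourth, selection after allocation is not inevitable. DSA comes before randomisation, so the judgement can be made in time. The blank-number rule and the full analysis set definition leave the later route open; they do not show that it will be used.

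**Conclusion.** The mismatch is real, relevant to safety and easily verified. One of three contraindications, together with one warning, has no counterpart in the eligibility criteria or the angiography record, while the other two contraindications do. Section 6.1.5 permits, but does not force, randomisation of patients whom 6.2.2 says not to treat, and practice may vary by site.

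The effect on the analysis is conditional. It arises if the contraindication is applied after allocation, and it could bias the comparison if that happens unequally between arms. The documents leave room for this because they do not state whether 6.2.2 covers the control device.

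A reader might want a number of affected patients. The documents give no prevalence of stenosis or stents near the clot, so none is offered. The conclusion does not depend on one.

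**What to change.** In one amendment, reconcile the abstract, 6.1.5.2, the Visit 2 DSA record in 6.2.1.3, 6.2.2.7 and 6.2.2.9. A stenosis or stent that is known, or visible on baseline imaging, should get the same answer in every section and for both arms. Which answer is a clinical choice for the sponsor and investigators.

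State in 6.1.6 that its rule on in situ stenosis covers stenosis first revealed after clot removal, and state whether 6.2.2 applies to the control device.

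Record the agreed item from the baseline DSA before randomisation, for example beside the existing questions on carotid occlusion, dissection, arteritis and tortuosity.

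The cost is amendment wording, one recorded item and possibly a few more screen failures, depending on how the conflict is resolved. No new test is needed, since DSA already precedes randomisation.

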6.2.2.8. Potential complications

Potential complications include, but are not limited to, the following:

- Hematoma and bleeding at the puncture site
- Vascular injury (e.g., perforation)
- Angiospasm
- Confusion
- Nervous system failure (including stroke and death)
- Ischemia
- Infection
- Aeroembolism
- Intracranial hemorrhage
- Vascular embolization
- Pseudoaneurysm formation
- Postoperative bleeding
- Distal embolization, including previously unaffected areas
- Adverse reaction to antiplatelet/anticoagulation agents or contrast media
- Device deformation, collapse, fracture or malfunction
- Thrombosis (acute and subacute)
- Arteriovenous fistula

6.2.2.9. Warnings

- Appropriate anti-platelet and anti-coagulation therapy should be used in accordance with standard guidelines.
- No twisting of the revascularization device
- For each new revascularization device, use a new microcatheter
- Electrical detachment cannot be performed during thrombectomy

- To prevent device detachment:
 - a. Do not use oversized device.
 - b. Do not withdraw the device if excessive resistance encounters. The device should be re-sheathed with a microcatheter and the entire system should be removed under aspiration. If resistance encounters during one more sheathing, stop entry and remove the entire system under aspiration.
 - c. Do not treat patients with pre-existing stenosis proximal to the thrombus site.
- The device is provided sterile and for single use. Do not re-use or re-sterilize. Reuse and re-sterilization increase the risks of patient infection and compromise device performance.

6.3. Monitoring Plan

The sponsor will entrust a contract research organization (CRO) for the monitoring of this trial, assign qualified CRA based on the complexity degree of this trial and the quantity of sites, and develop a corresponding monitoring plan, so as to ensure that the rights and interests of subjects are protected, data presented in trial records and reports is accurate and complete, and the trial is conducted in accordance with the approved protocol and relevant regulations.

Monitoring before the trial mainly includes: investigational device, study documents, trial personnel and trial training; monitoring during the trial mainly includes: regular visits, documents to be submitted to the Ethics Committee during the trial, monitoring of adverse events; monitoring after end of (or before prematurely terminating) the trial mainly includes: recovery and destruction of investigational products, EDC data entry and data query, validation of trial document integrity, notification of Ethics Committee, site closure and clinical trial report.

7. Statistical Analysis Method and Evaluation Method

7.1. Statistical Design, Method and Analysis Procedure

7.1.1. Statistical Design (Hypothesis Testing)

This study is a prospective, multicenter and randomized controlled design, with comparison type of non-inferiority test. It is to demonstrate that the investigational device also meets the needs of clinical application through comparison with the similar products that have been marketed, with the primary evaluation endpoint set as success rate of recanalization; the corresponding statistical hypothesis test is:

$$H_0 : p_T - p_C \leq -\Delta$$

$$H_1 : p_T - p_C > -\Delta$$

where, P_T is the expected success rate of recanalization in the test group; P_C is the expected success rate of recanalization in the control group; and Δ is the non-inferiority margin (taken as a positive value here).

7.1.2. Statistical Analysis Methods

7.1.2.1. General Principles

Statistical description: The categorical data are described as frequency and proportion; while the continuous data are described as mean, standard deviation, maximum, minimum, median, 25th quantile, and 75th quantile.

Statistical inference: For the comparison of general situation of the two groups, the quantitative indicators between groups are compared using group t test or Wilcoxon rank sum test according to the data distribution, classification indicators using chi-square test or accurate probability method (if the chi-square test is not applicable), and ordinal data using Wilcoxon rank sum test or CMH test.

All statistical tests, if not specified, are two-sided and the difference is considered statistically significant when P value is <0.05 (two-sided). In addition to the statistical methods listed below, detailed and additional exploratory analyses may be required and confirmed in the Study Reports and Statistical Analysis Plan (SAP).

7.1.2.2. Study Completion and Demographic Analysis

The number of subjects enrolled and the completion status of enrollment of each site should be summarized, and the dropout cases should be listed. Different data set sizes in each group, case distribution of each site, total dropout rate comparison and reasons for discontinuation, should be tabulated in detail. The demographic characteristics (age and gender), the relevant medical history and the treatment history of the patients are described, and the comparison of age and gender, etc. between the two groups will be conducted to measure the comparability between the two groups.

Demographic analysis is based on FAS.

7.1.2.3. Primary Efficacy Indicator

For the primary endpoint of recanalization success rate, at the level of $\alpha = 0.025$ (one-sided test) and $\beta = 0.2$, the success rate of target vessel recanalization in the study and control groups are compared, respectively. The 95% CI for their difference is calculated. If the lower limit of 95% CI for their difference is greater than -12.5%, it is considered that the test group is non-inferior to the control group. The inter-group comparison will be performed using the center effect-modified CMH chi-squared analysis, and the Logistics regression model can be considered for the inter-group comparison as appropriate to correct for the effects

of factors such as the center.

7.1.2.4. Secondary Efficacy Indicators

The secondary efficacy evaluation is based on Full Analysis Set (FAS) and Per-Protocol Set (PPS). For the statistical description and inference of the data, the applicable descriptive indicators and hypothesis test methods are selected based on the characteristics of the data.

7.1.2.5. Safety Indicator

The number and proportion of cases with normal conditions before treatment and abnormal conditions after treatment will be described respectively by the test group and the control group. AEs are described by the number and the incidence of AEs, where the likelihood ratio X^2 test or Fisher's exact probability test is used. Also, the manifestations and degree of AEs occurred in each group and their relationship to the investigational product will be described in detail.

